#### Safety population

The Safety population is defined as all subjects who received at least one dose of study medication.

#### **Antibody Population**

The antibody population will include those abaloparatide-SC treated subjects in the Safety population who have at least one post-baseline anti-abaloparatide antibody assessment.

### **Per-Protocol (PP) population**

The Per-Protocol (PP) population will include all ITT subjects who did not have any significant protocol deviations (PDs) (described in Section 2.2).

The PP population will be a supportive population for the efficacy analyses.

#### 2.2 **Protocol Deviation**

A protocol deviation (PD) is any change, divergence, or departure from the study design or procedures defined in the protocol. The PD categories related to study conduct are described in the Management of Protocol Deviations/Waivers section of the Medical Management Plan. PDs are recorded by the contract research organization (ICON) in their Clinical Trial Management System (CTMS). Subjects with at least one protocol deviation will be presented in a data listing, with indicators for key and non-key PDs (as defined in Appendix 1 of the Medical Management Plan, where a key PD is a deviation requiring reporting to the Functional Lead, Medical Monitor and or Sponsor). A summary table of the key PDs identified during the study will be presented.

Significant PDs are PDs that have the potential to impact the efficacy of the treatment on the subject.

The algorithm to determine significant PDs is in Appendix A of this SAP. Subjects with at least one significant PD will be excluded from the PP population. A Per-Protocol Memo with the algorithm in Appendix A together with the programming specification ("Per Protocol Population Data Set Development") will be developed and finalized prior to database lock to detail how each of the criteria in the algorithm can be programmed in SAS. The list of subjects with significant protocol deviations identified after applying the algorithm to the unblinded SDTM data after database lock will be reviewed and approved internally at Radius in a separate memo. A summary table of reasons for exclusion from the PP population will be presented. A data listing for subjects excluded from the PP population together with the exclusion reason(s) will be presented.

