8.3. Analysis Datasets

8.3.1. Populations for Analysis

The primary population for all efficacy analyses will be the Intention-to-Treat (ITT) Population, which is defined as all subjects randomized into this study. The primary population for safety analyses will be the Safety Population, defined as all subjects who received at least one dose of study medication. The Per-Protocol (PP) Population will include all ITT subjects who did not have any significant protocol deviations and will be used for supportive analyses. The criteria for the exclusion from the PP Population will be appropriately documented prior to database lock and treatment unblinding.

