8.7. Enrollment/Randomization/Masking Procedures

Abaloparatide-SC and placebo study medications will be prepared in a blinded fashion. Data will be reviewed in a blinded fashion and the analysis populations defined prior to database lock and unblinding.

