#### 1.2.3 Blinding

Abaloparatide-SC 80  $\mu$ g and placebo study medications will be prepared in a blinded fashion and will be supplied to the study sites in identical packaging. Information regarding treatment assignment will reside solely within the IRT, as part of the study blinding.

The central imaging laboratory responsible for measuring BMD will be blinded to treatment assignment throughout the study. Radius will not receive post-baseline BMD measurements until database lock.

The Pharmacokinetic (PK) samples and the blood samples for serum markers of bone metabolism (s-PINP and s-CTX) will be analyzed during study. The results of the PK and bone turnover markers data will only be provided to Radius after database lock.

In order to follow subjects who are antibody positive at their completion visit (Visit 9, or Visit 8 for early terminations), the appropriate procedures for maintaining the integrity of the study blind are documented in the Blind Management Plan for Immunogenicity Testing and the Immunogenicity Testing Operations Manual.

In the event of a medical emergency where the identity of study medication is necessary to appropriately treat the subject, the Investigator may unblind the subject's treatment through the IRT. Unblinding at the end of the study will occur after the data cleaning has occurred, the SAP has been finalized, and the database is locked.

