# Appendix A. Algorithm to Identify Significant Protocol Deviations that Exclude Subjects from the Per-Protocol (PP) Population

A protocol deviation is any change, divergence, or departure from the study design or procedures defined in the protocol. Significant PDs are a subset of PDs that have the potential to impact the effect of the treatment on the subject.

The below algorithm outlines the criteria for identifying significant protocol deviations. Subjects with at least one of these significant protocol deviations will be excluded from the PP population.

- A. Deviations of subject eligibility (Inclusion/Exclusion criteria) that will result in exclusion from PP population:
  - 1. Inclusion Criterion #2: A BMD T-score above the required level.
  - 2. Exclusion Criterion #2: A BMD T-score below the required limit.
  - 3. Exclusion Criterion #1: Presence of abnormalities of the lumbar spine that would prohibit assessment of spinal bone mineral density.
  - 4. Exclusion Criterion #3: Unevaluable hip BMD or subjects who have undergone bilateral hip replacement.
  - 5. Exclusion Criterion #4: Fragility fracture within the 12 months prior to signing of informed consent.
  - 6. Exclusion Criterion #5: History of severe vertebral fracture or > 2 moderate vertebral fractures.
  - 7. Exclusion Criteria #6, #8, and #10: Diseases and treatments affecting the bone strength.
  - 8. Inclusion Criterion #5: Laboratory tests affecting the bone strength
  - 9. Exclusion Criteria #18, #19, #20, #21, #22, #23, #24, #25, and #27. Prior treatment with bone acting agents within the specified time period.
- B. Deviations of study drug administration that will result in exclusion from PP population:
  - 1. The blinding of the study drug was broken during the subject's participation in this study before database lock.
  - 2. Duration of study drug exposure is less than 3 months (90 days)
  - 3. Compliance to study drug administration < 80%
- C. Deviations of efficacy measurements that will result in exclusion from PP population:
  - 1. Lumbar spine BMD is missing at baseline
  - 2. No post-baseline lumbar spine BMD measurements recorded
- D. Other significant protocol deviations
  - 1. Any protocol deviation with potential major impact on the primary efficacy endpoint will exclude a subject from the PP population. This will include subjects taking any prohibited medications during study.

Lab Parameter	Conventional Unit		SI Unit	
	Low	High	Low	High
Hematology				·

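### The SAP has the sponsor approve the Per-Protocol subject list on unblinded data after lock, contrary to the blinded review in Protocol 8.7, with one open-ended exclusion criterion and no declared change

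*SAP*

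**What the plan says.** Protocol Section 8.7 sets the general rule: "Data will be reviewed in a blinded fashion and the analysis populations defined prior to database lock and unblinding". Protocol Section 8.3.1 adds a rule for this population: "The criteria for the exclusion from the PP Population will be appropriately documented prior to database lock and treatment unblinding".

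SAP Section 2.2 works in two stages. First, a Per-Protocol Memo, containing the Appendix A algorithm and a programming specification, "will be developed and finalized prior to database lock to detail how each of the criteria in the algorithm can be programmed in SAS". Second, the list of excluded subjects "identified after applying the algorithm to the unblinded SDTM data after database lock will be reviewed and approved internally at Radius". A second memo records that approval.

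Appendix A holds the exclusion criteria. Its last item, D1, reads: "Any protocol deviation with potential major impact on the primary efficacy endpoint will exclude a subject from the PP population". It continues: "This will include subjects taking any prohibited medications during study".

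SAP Section 1.2.3 controls what the sponsor knows and when: "Radius will not receive post-baseline BMD measurements until database lock". Final unblinding "will occur after the data cleaning has occurred, the SAP has been finalized, and the database is locked". A signed PP list is not among those conditions.

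SAP Section 5 lists the changes from the protocol-specified analyses. The timing and blinding of the PP review are not on the list, and the closing sentence classes everything unlisted as an enhancement.

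**The concern.** PP analyses are useful only if nobody could have shaped membership with the results in view. Here the sponsor's review and approval of named subjects comes after lock, on unblinded data, when outcomes are also available. For a criterion that a program settles completely, this would matter little. For a criterion that asks whether a deviation could have had a major impact on the primary endpoint, it matters, because that judgement should be made without knowing the subject's arm or BMD response.

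What is at stake is the credibility of the supportive evidence. SAP Sections 4.3.1 and 4.3.2 repeat the primary and key secondary analyses in the PP population in order to back up the ITT findings. That backing is weaker if membership could have been influenced, even if nobody in fact influenced it. Because Section 5 is silent, a reader relying on it would not learn that the protocol's safeguard had changed.

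**Working it through.** The plan states no figure to reproduce, so the check compares the texts and counts what is affected.

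**1. Timing and blinding**

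| Step | Protocol | SAP | Consistent? |
|---|---|---|---|
| Exclusion criteria documented | Before lock and unblinding (8.3.1) | Algorithm and SAS specification final before lock (2.2) | Yes |
| Data review | Blinded (8.7) | Subject list reviewed on unblinded data (2.2) | No |
| Populations defined | Before lock and unblinding (8.7) | List produced and approved after lock (2.2) | No, if this means the subject list; yes, if it means criteria only |

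The second row is a contradiction however the third is read.

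**2. What the sponsor can know at approval.** Section 1.2.3 withholds post-baseline BMD only until lock, and Section 2.2 places the review after lock on unblinded data. Treatment and outcome can therefore both be known.

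**3. Room for judgement in Appendix A.** Items: A 9 + B 3 + C 2 + D 1 = 15. Fourteen cite a numbered eligibility criterion, a threshold (exposure under 90 days, compliance under 80%) or an observable event (blind broken, lumbar spine BMD absent). D1 does none of these: prohibited medication is named as included, not as the limit. Open-ended items: 1 of 15.

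A smaller gap is that B3 does not say which compliance calculation applies, whereas Section 4.5.1 requires both to be under 80%.

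**4. Is treatment identity needed?** None of the 15 items depends on the arm. Eligibility, exposure, compliance and presence of BMD are defined alike in both groups. A blind-break event can be flagged without saying what was revealed.

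**5. What is affected** (SAP Sections 4.3.1 and 4.3.2)

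- Primary and key secondary: (1 + 2) endpoints × 3 methods (pattern-mixture, MMRM, LOCF) = 9 PP estimates.
- Additional BMD endpoint-visits: lumbar spine 2 + total hip 2 + femoral neck 2 + ultra-distal radius 3 + distal one-third radius 3 = 12; 12 × 3 methods = 36 PP estimates.
- Time to new clinical fracture, also run in the PP population.
- ITT fixed-sequence tests (SAP Section 3.7): 0 of 3.

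**6. Declaration.** Section 5 records a change as small as adding one word to an endpoint name, but not this one.

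**The case against.** The strongest defence is that Protocol 8.7 requires populations to be defined, not subject lists to be signed. The rule specific to this population, in 8.3.1, concerns criteria only, and the SAP meets it. A full list before lock would also be awkward for the sponsor to produce, since item C2 depends on BMD data that it does not receive until lock. This stands as far as it goes: on the criteria-only reading, the timing conflict disappears. The conflict with blinded review does not.

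Secondly, the memo must show how each criterion can be programmed, and D1 is one of them, so D1 may be closed before lock. That is possible. The memo is not among the documents, so it cannot be confirmed, and the SAP text itself leaves D1 open.

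Thirdly, nothing says that reviewers may add or remove subjects, and approval could mean verification only. But the SAP does not limit approval to that or say what follows a disagreement with the program.

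Fourthly, the SAP requires a summary of exclusion reasons and a listing of every excluded subject, so a D1 exclusion would be visible. That is a real safeguard, but it gives transparency after the fact, not blinding.

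Finally, the PP population is only supportive, and one MMRM serves all visits of an endpoint, so the 36 are estimates rather than 36 separate models. Both points are right. They limit the consequence without removing the contradiction.

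**Conclusion.** The concern holds. Sponsor review and approval of the PP list on unblinded data after lock contradicts the blinded review in Protocol 8.7, item D1 is open-ended in the SAP text, and Section 5 does not declare the departure. The SAP does satisfy Protocol 8.3.1.

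The reach is 9 + 36 supportive PP estimates plus the PP fracture analysis. The ITT primary and key secondary tests, and their control at the 1% level, are not affected. The documents give no basis for a numerical bound on bias, and none is claimed. The size of the practical risk rests on one unknown, which is whether the pre-lock memo reduces D1 to a fixed, programmable rule. If it does, little discretion remains, and the main defects are an avoidable unblinded sign-off and a missing declaration. The point should be corrected, but it does not threaten the trial's main conclusion.

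**What to change.** Amend SAP Section 2.2, Appendix A and Section 5 as follows:

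1. Replace D1 with a closed, programmable list in the memo that is already planned. Alternatively, settle every D1 case by documented blinded review before lock, while post-baseline BMD is still withheld. State in the same memo which compliance rule B3 uses.
2. Run the fixed program with treatment codes masked and sign the PP subject list before unblinding. If exposure and compliance are final only at lock, run it on locked but still masked data. Take blind-break flags (B1) from the IRT log without treatment identity, and use present/absent flags for lumbar spine BMD (C1, C2). Add the signed list to the conditions for unblinding in Section 1.2.3.
3. After unblinding, permit only a mechanical re-run checked against the signed list, with no approval at subject level.
4. Declare any remaining departure from Protocol 8.7 in Section 5, including a masked run that takes place after lock.

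The cost is SAP wording, one closed list and moving one sign-off ahead of unblinding. No new data are needed.

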#### **3** GENERAL STATISTICAL METHODS

### 3.1 Sample Size Planned and Specified in the Protocol

A study sample size of 225 subjects (150 in the abaloparatide-SC group and 75 in the placebo group) will provide at least 99% power to detect a mean difference of 6.5% in the percentage change from baseline in lumbar spine BMD at 12 months between the abaloparatide-SC and the placebo groups at a two-sided alpha level of 0.01, assuming a standard deviation (SD) of 6.0% and a drop-out rate of 10%. For the key secondary endpoints, a total sample size of 225 subjects will have 96% power to detect a 2.2% mean difference (SD=3.5%) of percent change in total hip BMD at 12 months, and 80% power to detect a 2.0% mean difference (SD=4.1%) of percent change in femoral neck BMD at 12 months.

#### 3.2 General Methods

Summary tables will be presented by treatment group (abaloparatide-SC and placebo) and overall, when appropriate. For categorical data, summary tabulations of the number and percentage of subjects within each category of the parameter will be presented. When tabulating categorical data, "missing" will be included as a category and the number of subjects with missing data will be presented. For continuous data, the number of subjects, mean, median, standard deviation (SD), minimum, interquartile range (Q1 and Q3), and maximum will be presented.

All data listings that contain an evaluation date will contain a relative study day. Screening, pretreatment, and on-treatment study days will be numbered relative to the day of the first dose of study medication which is designated as Day 1. Study days prior to the first dose of study drug will be calculated as: [date of assessment – date of first dose of study drug]. Study days on or after the first dose of study drug will be calculated as: [date of assessment – date of first dose of study drug + 1].

Where applicable, confidence intervals about a parameter estimate will be presented using the same number of decimal places as the parameter estimate and p-values will be rounded to 4 decimal places prior to assessment of statistical significance.

If the date of last dose is missing, then the earlier of the following 2 dates will be used as the last dose date for analysis and summary purposes: the final visit/early termination visit date or the last study drug dispense date + 30 days.

For subjects in the abaloparatide-SC group, the serum samples for immunogenicity testing will be analyzed and reported separately. All the planned efficacy and safety analyses related to immunogenicity results and antibody status described in this SAP will be reported separately.

This study is being conducted during the COVID-19 pandemic. The COVID-19 outbreak emerged in December 2019 quickly became a global pandemic as declared by the World Health Organization in early March 2020. At that time, a variety of mitigations to assure safety of participants and address operational issues were implemented by Radius. To investigate the effect of the COVID-19 pandemic on study conduct, additional analyses comparing the subjects who completed or withdrew from the study before the onset of the COVID-19 pandemic, i.e, before 01 March 2020, with the subjects who were ongoing or randomized during the COVID-19 pandemic, i.e, on or after 01 March 2020, will be conducted where applicable.

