5.4. Dosing and Administration

Subjects will self-administer a single daily dose of 80 μ g of study medication during the Treatment Period.

The first self-administration is to occur at the study site under observation. On the days of clinic visits, study medication **must be administered in the clinic** to accommodate preinjection and post-injection procedures; study personnel may administer the study medication. For the Month 12 visit, subjects should be instructed to bring the study drug dispensed at the last study visit and to administer the study drug onsite.

Subjects will be trained by study personnel during the Pretreatment Period how to self-inject study medication with the abaloparatide-SC/Placebo injection pen. If a subject requires assistance with study medication administration, an individual (e.g., a family member) who has been trained by study personnel may provide assistance.

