Subjects will be instructed to use a new pen after each 30-day period. At each clinic visit during the Treatment Period, the used and unused abaloparatide-SC or placebo injection pens must be returned. Compliance, AEs, and use of concomitant medications should be reviewed upon drug re-supply and documented accordingly in the drug accountability log and eCRF.

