6.2. Study Schedule

This study is comprised of 9 clinic visits. Study assessments are to be performed according to the Schedule of Assessments and Procedures (Table 3). There is $a \pm 4$ -day window for each clinic visit.

The study will consist of a Screening Period (up to 2 months), a Pretreatment Period (1 week), a Treatment Period (12 months), and a Follow-up Visit (1 month). During the Treatment Period, subjects will have clinic visits for study-related protocol procedures at Day 1, Month 1, Month 3, Month 6, Month 9, and Month 12. The active phase of the study will be considered complete when the last subject undergoes the last visit. For the purpose of this study, 1 month is equal to 30 days.

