6.2.13. Visit 8 (Month 12)/Early Termination Visit

- Symptom-directed physical examination, including assessment for potential vertebral fracture
- Collect blood for immunogenicity testing
- ECG
- Weight
- Height
- Orthostatic blood pressure and vital signs
- Only for subjects who consent to provide PK samples and attend the Month 12 visit: Collect a predose sample within 10 minutes before injection
- Self-administration of study medication when directed by site staff after completion of predose activities using medication dispensed at Visit 7 (Note: Applicable only to subjects completing a Month 12 visit)

- Only for subjects who consent to provide PK samples and attend the Month 12 visit: Collect a postdose sample at 1.5 hours (±0.5 hour) after injection
- PTH, 25-hydroxyvitamin D, and 1,25-dihydroxy vitamin D level
- Laboratory testing of serum biochemistry, hematology, coagulation and urine dipstick
- BMD assessments of lumbar spine, total hip, femoral neck, and wrist by DXA
- Measurement of volumetric bone density at the hip by QCT
- Bone turnover markers (s-PINP and s-CTX)
- Serum total testosterone and SHBG
- Clinical assessment of new fractures
- AE and concomitant medication review
- Review subject diary

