The duration of study drug exposure, duration category in months ( $\leq 1$  month,  $1 < to \leq 3$  months, 3 to  $\leq 6$  months, 6 to  $\leq 9$  months, and > 9 months), number of doses delivered, and percent compliance to study drug administration will be summarized by treatment group for the Safety, ITT, and PP populations.

To evaluate the relationship between study drug exposure and the antibody status, the duration of study drug exposure and percent compliance to study drug administration will also be summarized by antibody status (ADA-, ADA+/Nab+, ADA+/Nab-, All ADA+, and Overall) using the Antibody Population.

If a subject is shown to be <80% compliant with study drug administration using both calculations of study drug administration compliance, this subject will be considered as having a significant protocol deviation and thus excluded from the Per-Protocol Population.

Subjects' drug exposure and compliance will be carefully reviewed against the onset of the COVID-19 pandemic. Each subject's study drug exposure and compliance prior to 01 March 2020 and on or after 01 March 2020 will be calculated based on information collected from the subject diary:

- For subjects with last dose date prior to 01 March 2020 and subjects with first dose date on or after 01 March 2020, their duration of study drug exposure (days), number of doses delivered, and percent compliance to study drug administration relative to 01 March 2020 will be calculated as above based on missed doses in subject diary.
- For subjects who started taking the study drug prior to 01 March 2020 and continued on or after 01 March 2020, their duration of study drug exposure and compliance before 01 March 2020 and on or after 01 March 2020 will be calculated as follows:
  - Duration of study drug exposure relative to 01 March 2020:
    - Duration before 01 March 2020 = 29 February 2020 date of first dose + 1
    - Duration on or after 01 March 2020 = Overall duration of study drug exposure duration before 01 March 2020; where overall duration of study drug exposure = last dose date – first dose date + 1
  - The number of doses delivered relative to 01 March 2020:

- Number of doses delivered before 01 March 2020 = A {B + ([C x D] / E)}, and will be rounded to the nearest integer; where:
  - A = Duration of study drug exposure before 01 March 2020
  - B = Total number of missed doses from pens dispensed before 01 March 2020 and with scheduled return dates before or on 01 March 2020

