  - C = Number of missed doses from pens dispensed during the last drug dispensing visit prior to 01 March 2020 but with scheduled return date after 01 March 2020
  - D = 01 March 2020 last drug dispensing date prior to 01 March 2020
  - E = (number of dispensed pens during the last drug dispensing visit prior to 01 March 2020 - 1) x 30.
- Number of doses delivered on or after 01 March 2020 = Number of doses delivered during whole study – number of doses delivered before 01 March 2020.
- The percent compliance (%) to study drug administration relative to 01 March 2020:
  - Percent compliance before 01 March 2020 = (Number of doses delivered before 01 March 2020 / Duration of study drug exposure before 01 March 2020) x 100%
  - Percent compliance on or after 01 March 2020 = (Number of doses delivered on or after 01 March 2020 / Duration of study drug exposure on or after 01 March 2020) x 100%.

The study drug exposure and percent compliance to study drug administration before 01 March 2020 and on or after 01 March 2020 will be summarized by treatment group respectively.

The study drug exposure and compliance will also be summarized based on subject study status during the pandemic (completed or withdrew from the study before 01 March 2020 vs ongoing on or after 01 March 2020) and by region (North America and Europe).

All study drug administration and accountability data will be listed by treatment, study site, and subject number.

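### SAP 3.2 caps a missing last-dose date at one pen (30 days) after the last dispensing, which is too early for a man who kept dosing from a 60- or 90-day supply up to a later final or early termination visit

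*SAP*

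**What the plan says.** SAP 3.2 (General Methods) replaces a missing last-dose date by the earlier of two dates: "the final visit/early termination visit date or the last study drug dispense date + 30 days". It gives no reason for the 30 days.

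On supply, Protocol 5.1.1 describes a pen holding 30 once-daily doses, and Protocol 5.4 states: "Subjects will be instructed to use a new pen after each 30-day period". Protocol 6.2 states: "For the purpose of this study, 1 month is equal to 30 days". It also allows a ± 4 "day window for each clinic visit". The visit lists in Protocol 6.2.8 to 6.2.12 include dispensing at Day 1 and Months 1, 3, 6 and 9. The Month 12 list (6.2.13) has none; for that visit, under Protocol 5.4, "subjects should be instructed to bring the study drug dispensed at the last study visit and to administer the study drug onsite". Section 6.2.13 names Visit 7 (Month 9) as the source of that dose.

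SAP 4.5.1 treats a dispensing as a set of pens with a return date. Its COVID-19 compliance split refers to "pens dispensed before 01 March 2020 and with scheduled return dates before or on 01 March 2020" and to pens from the last dispensing before that date "but with scheduled return date after 01 March 2020".

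The last-dose date sets exposure duration and the compliance denominator (SAP 4.5.1), the end of the treatment-emergent adverse event (TEAE) window at 30 days after the last dose (SAP 4.5.3), and the end of the concomitant-medication window (SAP 4.5.9).

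**The concern.** The 30-day term matches one pen, which is the Day 1 supply. After Month 1 a man must hold more than one pen to dose daily until his next visit. Because the rule takes the earlier date, an ET visit that documents a man's later presence cannot move his imputed last dose beyond 30 days after dispensing.

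What is at stake is safety tabulation more than efficacy. If the date is too early, the TEAE window closes too early, and an event that began while he was still injecting goes into the non-TEAE table. His exposure is also shortened, and his pen-based compliance is divided by too small a number.

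**Working it through.** **Inputs.** Nominal study days follow from 30-day months: dispensing on Days 1, 30, 90, 180 and 270, and Month 12 on Day 360. Visits may move 4 days either way; Day 1 is fixed. Daily dosing up to the next scheduled visit is assumed.

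**The plan's own figure.** 30 doses per pen ÷ 1 dose per day = 30 days, so the 30-day term is exactly one pen.

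**Shortfall of the imputed date** = next visit day − (dispensing day + 30). **On-treatment days outside the imputed TEAE window** = next visit day − (dispensing day + 60).

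| Last dispensing | Next visit | Shortfall, nominal (range with windows) | Days outside TEAE window |
|---|---|---|---|
| Day 1 | 30 | 30 − 31 = −1, none (at most 34 − 31 = 3) | none |
| Month 1, Day 30 | 90 | 90 − 60 = 30 (86 − 64 = 22 to 94 − 56 = 38) | 90 − 90 = 0 (at most 94 − 86 = 8) |
| Month 3, Day 90 | 180 | 180 − 120 = 60 (176 − 124 = 52 to 184 − 116 = 68) | 180 − 150 = 30 (22 to 38) |
| Month 6, Day 180 | 270 | 270 − 210 = 60 (52 to 68) | 270 − 240 = 30 (22 to 38) |
| Month 9, Day 270 | 360 | 360 − 300 = 60 (52 to 68) | 360 − 330 = 30 (22 to 38) |

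These are the largest shortfalls. If he stopped sooner, the shortfall is his true last-dose day − (dispensing day + 30), and it is zero if he stopped within 30 days of dispensing.

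**Worked case.** Last supplied on Day 270, dosed daily to an ET visit on Day 350, date not recorded.
- Imputed last dose: min(350, 270 + 30) = Day 300, which is 50 days early.
- TEAE window closes on 300 + 30 = Day 330 instead of 350 + 30 = Day 380. An event starting on Day 340, while he was dosing, is a non-TEAE.
- Pen compliance, all pens measured: 350/300 = 116.7%.

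**Per-Protocol set.** SAP Appendix A excludes exposure below 90 days. A man with a 60-dose Month 1 supply from Day 30 takes the last dose on Day 89, so his true exposure is 89 days and exclusion is right anyway. From the Month 3 supply on, imputed exposure is at least 86 + 30 = 116 days. Under the 80% compliance rule in SAP 4.5.1, both calculations must fall below 80%. A case can be built (245 doses in 350 days is 70%, but 245/300 = 81.7% by pen), but it needs a missing date together with poor compliance.

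**The case against.** The strongest defence is that a fallback stop date and the length of a supply answer different questions. A man with no recorded last dose may well have stopped soon after his last visit, and taking the earlier of two dates is a recognisable cautious convention. This stands for men with no later visit: nothing shows that they kept dosing, and they have few or no later events to misplace. It does not stand for men who attended a final/ET visit. A date that is cautious for exposure is not cautious for TEAEs, and the SAP leans the other way elsewhere: in Appendix D, an event whose start date remains missing is counted as treatment-emergent.

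A reader might infer three stronger points that the documents do not support.
- *That SAP 4.5.1 contradicts SAP 3.2.* It does not. The terms in 4.5.1 apportion missed doses around 1 March 2020; they do not estimate when dosing stopped. They show only that the SAP expects several pens per dispensing.
- *That Month 12 completers are routinely misdated.* If Month 9 was the last dispensing, the rule indeed cannot return the Month 12 date (latest 274 + 30 = Day 304; earliest visit Day 356). But completers dose on site under supervision, so their date should be known.
- *That Per-Protocol membership shifts materially.* The check above shows only narrow, constructed cases.

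It is also fair to say that pen counts per visit are not in the documents (the dispensation plan is in the Pharmacy Manual), so 60 and 90 days are inferred from visit spacing. Home delivery (Protocol 5.2.1 and 6.2.1) could move a dispensing date and reduce the shortfall.

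**Conclusion.** The point holds as a minor correction. For a man with a missing last-dose date who kept dosing to a final/ET visit more than 30 days after a Month 1, 3, 6 or 9 dispensing, SAP 3.2 gives a date that is too early: nominally by up to 30 days for the Month 1 supply and 60 days for the later ones. The consequences are understated exposure, possible pen compliance above 100%, a shortened concomitant-medication window, and events in nominally the last 30 days of a 90-day supply tabulated as non-TEAEs. Those events remain in the non-TEAE table and the listings.

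This rests on supplies that cover the interval between visits and on dispensing at clinic visits. The number of men concerned is not given and is probably small, since it takes a missing date, continued dosing and a later visit. The primary intention-to-treat analysis does not use this date, the Per-Protocol set is supportive, and the safety analyses are essentially descriptive.

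**What to change.** Replace the sentence in SAP 3.2 with:

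> If the date of last dose is missing and a final/ET visit took place, use the earlier of that visit date and the end of the period the last dispensing was meant to cover (the next scheduled dispensing or Month 12 visit). If no final/ET visit took place, use the last dispensing date + 30 days. A last-dose date documented in the diary takes precedence where one exists.

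Flag imputed dates in the exposure listing. The diary clause will not help everyone: Protocol 5.4 expressly asks for dose dates and times only on Days 2 to 7 of Months 1 and 9. Pen measurements should not be used to date the last dose, because they give only a count.

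In the worked case the new rule gives min(350, 360) = Day 350, as it should.

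The cost is one sentence and one flag, plus an error in the other direction for an ET attendee who stopped early in a supply and has no documented date. Suppose he was supplied on Day 270, stopped on Day 280 and attended ET on Day 350. Exposure is over by 300 − 280 = 20 days now and by 350 − 280 = 70 days after the change. The TEAE window closes on Day 330 now and Day 380 after, against a true 280 + 30 = Day 310, so some off-treatment events would count as TEAEs. Keeping 30 days for men without a final/ET visit avoids extending that error to them.
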